Many burn centers have revised their policy during COVID-19 pandemic (5),(6). Burns are an acute emergency condition, and burn management needs to be initiated before COVID-19 infection status can be confirmed. Our institute already developed an algorithm for protection during COVID-19 infection. However, anesthesia management is challenge for burn patient particularly if the patient is suspected or diagnosed to be positive for corona virus.

In the era of COVID-19, Both the American Society of Regional Anaesthesia and Pain Medicine (ASRA) and the European Society of Regional Anaesthesia and Pain Therapy (ESRA) established a joint statement which recommends neuraxial and peripheral nerve blocks for patients with COVID-2019 infection and describe the benefits of regional anesthetic and analgesic techniques over general anaesthetics especially in patients with underlying metabolic derangements such as burns (7). Those critical patients with COVID-19 were subjected to coagulation abnormalities which may affect their survivals (8).

Aim of our Study:

Primary outcome is to investigate survivals, ICU admission and length of hospital stay of those critical patients.

Secondary outcome is to analyses perioperative factors that affected their survival outcome.

4. Objectives

In this section provide a clear statement of the primary and any secondary objectives of the study

To investigate survivals, ICU admission and length of hospital stay of those critical patients.

And to analyze perioperative anesthetic factors that affected their primary outcome.

5. Indicate if this is a retrospective data review

- **Retrospective Chart/data Review** *(Retrospective means the data is already in existence when the project is submitted to the IRB for initial review.)*
- **Provide the date range of the chart review** *(if this is a retrospective chart review, the end date must come before the submission date April 1, 2020, and November 16, 2020.)*

6. Study Methodology

Patients who had the burn graft surgery at Al Wakrah Hospital; Hamad Medical Corporation between from April 1, 2020, and November 16, 2020. **Planned sample size will include all COVID-19 positive and negative cases. Our institution as Al Wakrah Hospital is the ONLY center at HMC which deals with those unique Burn patients allover Qatar. By increasing sample size, we can get our expected results statistically.**

Data Source

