The electronic medical record (Cerner) used in order to identify patients who match study defined criteria. We can Collect data directly from Cerner to excel sheet

Variable Abstraction

Patient demographic and clinical data will be collected including age, morbidities, presenting symptoms, physical examination, laboratory investigations, intraoperative data, type of surgery, postoperative course, survival, and length of hospital stay and follow up.

In addition, the type of anesthesia is also included as factor for further complications ex general anesthesia, spinal or combined spinal epidural type.

Retrospective full reviewing of their medical illness and chart laboratory and investigations will be collected after getting approval of MRC and IRB committee.

7. Study Population and Study Setting/ Location

All adult patients who had undergone burn graft surgery at Al Wakrah (AWH) Hospital; Hamad Medical Corporation between April 1, 2020, and November 16, 2020. We will include all Consecutive Adult patient underwent burn grafting surgery at AWH either

they are COVID positive or negative.

8. Study procedures

Provide an outline and describe in detail the processes and operations of the study, including logistics

Study Duration and Timelines

Expected duration of the study & start times, stages of the study such as screening, treatment phase, visit numbers, etc

6 months data collection & another 6 months writing manuscript and trial to submission to a suitable journal

Informed Consent

Informed Consent will be waived for such a retrospective analysis.

Risk

This study has no physical, psychological, economic or societal harms that may befall a subject as a result of their data being included in this study.

Bio-Specimens & Sample Collection

Not applicable

Outcomes

Primary outcome is to investigate survivals, ICU admission and length of hospital stay of those critical patients.

Secondary outcome is to analyses perioperative anesthetic factors that affected their primary outcome.

Data Collection, Management&Confidentiality

a) Indicate below HOW study data will be collected for the proposed research.

Study Forms Study Database Study Web-Based/App Other

Please detail how study data will be coded:

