Special encryption codes will be used to separate research data from subject identifiers and the data will be dealt with privacy and confidentiality. Each patient will be assigned a random code and any information relating to the patient will now only be related to the patient by the random code and not by their name or health card number. Then any link to the actual record will be destroyed after data collection is completed. The anonymized data set will be kept for at least 5 years after study completion. Data will be collected in excel format.

b) Describe below WHERE and HOW the study data is physically stored.

Primary investigator will store the electronic data on a password protected computer which is secured by a firewall. Data collection form will be kept in a safe cabinet. The anonymized data set will be kept for at least 5 years after study completion.

kept in a safe cabinet

c) Describe below WHO controls access to the study data

PI

d) Describe below WHO has access to the study data.

PI

e) Describe below HOW the study data is accessed.

The lead PI will have the control over the access to study data through password secured computers.

f) Will subject identifiers be shared outside of HMC? If YES describe below WHOM the study data is shared

No

Subject Withdrawal/ Withdrawal of Consent

Not applicable

9. Statistical Consideration and Data Analysis

Descriptive statistics will be used to summarize all demographic, clinical, laboratory

tests, intraoperative data, postoperative course and outcomes. The normally distributed data and results will be reported with mean and standard deviation (SD); the remaining results will be reported with median and interquartile range (IQR). Categorical data will be summarized using frequencies and percentages.

Survival can be performed using Kaplan Meir Curve; risk factors can be identified by using Univariate Analysis and Multivariate Logistic Regression Analysis.

All P values presented will be two-tailed, and P values <0.05 will be considered as statistically significant. All Statistical analyses will be done using statistical packages SPSS 22.0 (SPSS Inc. Chicago, IL) and Epi-info (Centers for Disease Control and Prevention, Atlanta, GA) software.

10. Adverse Event Reporting

No adverse events are expected.

11. Ethical Consideration

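### Section 9 calls every P value below 0.05 significant over an open list of factors and an inconsistent set of outcomes, so the chance of a false risk factor is unstated and well above 5%

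*Combined protocol and SAP*

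**What the plan says.** **Threshold.** Section 9 sets one rule for all results: "All P values presented will be two-tailed, and P values <0.05 will be considered as statistically significant". It names no lead outcome, adjustment, order of testing or exploratory status.

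**Method.** The same section says that "risk factors can be identified by using Univariate Analysis and Multivariate Logistic Regression Analysis". It gives no rule for selecting factors and no limit on their number.

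**Outcomes.** Section 8 puts three endpoints under one label: "Primary outcome is to investigate survivals, ICU admission and length of hospital stay of those critical patients".

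**Scope of the factor analysis.** There are two versions.
- Sections 1 and 3: "Secondary outcome is to analyses perioperative factors that affected their survival outcome".
- Section 8, with Section 4 to the same effect: "Secondary outcome is to analyses perioperative anesthetic factors that affected their primary outcome".

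**Candidate variables.** Section 6 (Variable Abstraction) gives an open list: "including age, morbidities, presenting symptoms, physical examination, laboratory investigations, intraoperative data, type of surgery, postoperative course". It then adds that "the type of anesthesia is also included as factor for further complications".

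**The concern.** A flat 0.05 threshold limits the error of one test. Here it applies to an unspecified number of tests, and any that falls below it may be reported as a risk factor. A reader of Section 9 would take the error rate to be 5%, when the rate for the whole set of factor tests is higher and cannot be worked out from the plan.

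The multivariable step does not cure this. It retests the factors on the same patients, so a chance association that passes the univariate step often passes the next.

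The conflicting scopes add to the problem. With two versions of which factors are set against which outcomes, the choice can be made after the results are seen. Section 6 looks to a larger sample to deliver the expected results, but at a fixed threshold of 0.05 a larger sample does not lower the false-positive rate. At stake is whether a chance finding is published as a factor that influenced survival, intensive care use or stay.

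**Working it through.** **Inputs from the plan**
- Threshold: 0.05, two-sided, for every P value (Section 9).
- Outcomes called primary: 3 (Section 8).
- Classes of variable in Section 6: 8 in the open list (postoperative course included), plus type of anaesthesia, making 9.
- Number of tests k, sample size and number of events: not stated. The values below are assumptions.

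The only design figure is the 0.05 threshold. One test returns 1 − 0.95 = 0.05, so there is nothing further to reproduce.

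**Step 1. Chance of at least one false significant result**

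If no factor matters and tests are independent, the chance is 1 − 0.95^k and the expected number of false positives is 0.05 × k.

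| Reading | k | Chance of at least one | Expected number |
|---|---|---|---|
| Type of anaesthesia × 3 outcomes | 3 | 1 − 0.95^3 = 14.3% | 0.15 |
| 9 classes, one variable each, × survival | 9 | 1 − 0.95^9 = 37.0% | 0.45 |
| 9 classes × 3 outcomes | 27 | 1 − 0.95^27 = 75.0% | 1.35 |
| 20 variables × 3 outcomes | 60 | 1 − 0.95^60 = 95.4% | 3.0 |

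The chance passes one half at 14 tests (1 − 0.95^14 = 51.2%).

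**Step 2. Allowing for correlation**

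Correlated normal test statistics were simulated (100,000 draws per setting). For 9 factors × 3 outcomes:
- outcomes correlated 0.5, factors independent: 70%
- factors 0.3, outcomes 0.5: 64%
- both 0.5: 56%
- factors 0.5, outcomes 0.7: 50%

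For 20 factors against survival alone, the chance is 64% if independent, 54% at factor correlation 0.3 and 42% at 0.5.

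**Step 3. Rare deaths**

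With few deaths, Fisher's exact test on a binary factor runs below its nominal 5%. For an assumed 10 deaths in 100 patients its true size is 2.6%, 3.0% and 1.6% at factor prevalences of 20%, 30% and 50%. Ten such independent tests give 23%, 26% and 15%, against 40% at the full 5%.

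**Step 4. Does the multivariable step remove false factors?**

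Pure-noise data were passed through univariate P<0.05 and then multivariable P<0.05, for one outcome. The two-step rule is itself an assumption, since Section 9 names both analyses but not how they connect.

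| Assumed setting | 8 candidates | 20 candidates |
|---|---|---|
| 80 patients, 30% events, continuous factors, independent | 30% | 57% |
| Same, factor correlation 0.3 | 25% | 39% |
| 80 patients, 10% events, continuous | not run | 52% |
| 50 patients, continuous (30% events) | not run | 51% |
| 80 patients, 5 deaths, binary factors at 20% prevalence | 19% | 38% |

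Entries are the share of datasets with at least one false independent factor. Repeat runs differ by a few percentage points. In the first row the median false odds ratio is about 1.9 per standard deviation, a figure that applies only to continuous factors.

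**The case against.** A reader might infer that a false risk factor is likely, that is, more probable than not. The documents do not establish this. It needs the full variable list set against all three outcomes, and no sentence makes that pairing: the broad wording on factors goes with survival, and the three outcomes go with anaesthetic factors. On the narrower readings the chance is about 14% or 37%, and rare deaths lower the survival part further.

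Section 6 can also be read as a list of data to abstract, much of which Section 9 only summarises. This has some force, since Section 9 does not say that every field is tested. But Section 6 says that type of anaesthesia is included as a factor as well, which suggests that the preceding items are candidates too. Several classes, such as laboratory tests and morbidities, would normally hold more than one variable.

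A reader might also infer that the primary objective involves three competing significance tests. It does not: Section 9 gives that objective descriptive summaries and a Kaplan-Meier curve. The three outcomes multiply error only through the factor analysis.

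Finally, formal adjustment of secondary associations in a single-centre retrospective chart review is partly a matter of preference. That is fair for work presented as exploratory. This plan gives no such label, speaks of identifying factors that affected outcome, and calls every result below 0.05 significant.

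**Conclusion.** The point holds as one about uncontrolled and undefined testing. Across the readings the plan allows, the chance of at least one false significant factor when nothing matters runs from about 14% to about 95% with independent tests. For nine classes against three outcomes it is about 50 to 70% under the correlations tried. On noise, the two-step screen gives a false independent factor for one outcome in roughly 20 to 57% of datasets.

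All these figures rest on assumed numbers of tests, patients and events, and on assumed factor types and correlations. No single value can be attributed to the plan, and a better-than-even chance is not shown. What is secure is that the plan does not say which tests count, and that the listed readings in Step 1 give roughly three to nineteen times the 5% that Section 9 suggests (14.3 / 5 = 2.9; 95.4 / 5 = 19.1). The study remains feasible; what changes is what it may conclude.

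**What to change.** In Section 9, with matching wording in Sections 1, 3, 4 and 8:

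1. Reconcile the two scope statements. Before analysis, fix a short list of perioperative factors, including type of anaesthesia, and the outcome or outcomes each is tested against.
2. Report univariate results as descriptive. Report all factor-outcome associations as exploratory, with effect estimates and 95% confidence intervals: odds ratios for binary outcomes and a suitable measure for length of stay. Do not describe them as identified risk factors or as factors that affected outcome.
3. Wherever significance is still claimed, apply Benjamini-Hochberg at 5% within each outcome in place of the flat threshold. If nothing matters and tests are independent, this gives 5% per outcome. Over three independent outcomes that is 1 − 0.95^3 = 14%, against 75% for 27 unadjusted tests.

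Making type of anaesthesia the only tested factor would also limit the error, but it would redefine the objectives and is not needed.

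The cost is wording and a one-line P-value adjustment, with no new data. The downside is that fewer factors can be called significant.
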